Current guidelines for treatment of GAD include medication, cognitive behavioral therapy (CBT), or both. Most medications show moderate initial efficacy, but benefits often decrease over time. Benzodiazepines (BZs), which are GABAA receptor agonists, are the most effective for treating GAD (Hedges'  $g$  (effect size) of ~0.50; where  $g=0.2$ , 0.5, and 0.8 are generally considered small, moderate, and large effect sizes, respectively). However, guidelines recommend only prescribing BZs for short-term use due to the potential to develop tolerance and dependence. Recommended medications for long-term use include antidepressants (selective serotonin reuptake inhibitors (SSRIs) and serotonin-norepinephrine reuptake inhibitors (SNRIs)), which are also recommended for other anxiety disorders. However, SSRIs and SNRIs have only modest effectiveness for treating GAD (Hedges'  $g=0.33-0.36$ ). Also, these medications take several weeks to reach maximum efficacy and have common, undesirable side effects, including headaches, nausea, agitation, difficulty sleeping, and sexual dysfunction, which substantially impact medication adherence and discontinuation. As a non-pharmaceutical treatment, CBT has distinct advantages for patient acceptability, but CBT also has modest effectiveness (Hedges'  $g=0.3-0.5$ ). Taken together, GAD remission rates are relatively low for current first-line therapies.

[figure not shown]

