### 5.2 Secondary Endpoints

The following secondary endpoints will be evaluated:

- Feasibility: For each treatment group, the percentage of treatment sessions that provide effective nerve stimulation as assessed via participant-reported confirmation of tingling sensation
- Acceptability: For each treatment group, the overall satisfaction with treatment (via 100-mm VAS)
- Effectiveness:
  - Effect of treatment group on change in clinician-assessed anxiety severity (via HAM-A)
  - Effect of treatment group on change in weekly participant-reported anxiety severity (via BAI)
  - Effect of treatment group on change in participant-reported GAD symptoms (via GAD-Q-IV)
  - Effect of treatment group on change in daily self-reports for anxiety severity (via 100-mm VAS)
  - Effect of treatment group on change in self-reports of anxiety severity immediately after vs. before treatment (via 100-mm VAS)
  - Effect of treatment group on change in daily self-reports for anxiety interference with daily living (via 100-mm VAS)
  - Effect of treatment group on medication use (via self-reports)
  - Effect of treatment group on change in clinician-assessed depression severity (via HAM-D)
  - Effect of treatment group on change in participant-reported depression severity (via PHQ-9)
  - Effect of treatment group on change in participant-reported PTSD severity (via PCL-5)
  - Effect of treatment group on change in sleep quality (via PSQI survey)

- Effect of treatment group on change in quality of life (via SF-12 survey)
- Blinding: For each treatment group, the blinding index and 95% confidence interval (via Bang et al. blinding assessment method)

All of these secondary endpoints provide valuable information on the effectiveness of the Empower Neuromodulation System for GAD treatment as well as the acceptability to the intended patient population.

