## 8 STUDY PROCEDURES

### 8.1 Method of Assigning Participants to Treatment Groups

This is a randomized, controlled study. At enrollment participants will be randomized (1:1, [REDACTED] to the active or sham treatment group. Men and women will be randomized separately to ensure that the distribution of men and women in the active and sham arms are consistent. Women account for approximately 64% of American adults with GAD. Thus, to ensure that we enroll a study cohort that is both representative of the American patient population and provides a sufficient sample size of both sexes to

exploratorily evaluate sex as a biological variable, we will enroll a maximum of 21 women and a maximum of 12 men.

[figure not shown]
Participants will also be randomized for the body side that they should apply stimulation to first [REDACTED]

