## 10 EVALUATIONS BY VISIT

### 10.1 Visit 1 (Day 1)

1. Review the study with the participant and obtain written informed consent and HIPAA authorization and assent
2. Assign the participant a unique screening number
3. Record demographics data
4. Record medical history
5. Record concomitant medications
6. Perform an abbreviated physical examination
7. Perform an abbreviated psychiatric examination, including M.I.N.I. and C-SSRS-R
8. Collect urine sample and perform a urine pregnancy test, if applicable
9. Perform clinician-administered assessments (HAM-A and HAM-D) and participant-reported survey (PCL-5)
10. Final review of eligibility
11. Complete self-report surveys (GAD-Q-IV, PHQ-9, PSQI, SF-12)
12. Randomize participant
13. Train participant on Empower device, smartphone, and app.
14. Self-administer a treatment session and complete app-based surveys (BAI, medication use, anxiety severity and interference, skin tingling)
15. Record adverse events, if applicable
16. Schedule participant for Visit 2 in 14 days

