#### 15.4 Analysis of Secondary Endpoints

Secondary endpoints will be analyzed via the methods described below. Unless otherwise noted, for daily and weekly metrics, we will use a random-intercept linear mixed model with restricted maximum likelihood to compare results between the active and sham treatment groups. As a secondary analysis for each of these endpoints, we will evaluate the correlations for duration since last benzodiazepine dose and dose amount vs. the endpoint. If this relationship is significant for an endpoint, we will include time since last dose in our statistical analysis.

Feasibility: Effective nerve stimulation: We will calculate effective nerve stimulation (treatment sessions that elicit skin tingling as a percentage of total treatment sessions) for each participant. We will also compare effective nerve stimulation between the active and sham treatment groups (t-test).

Acceptability: Overall satisfaction with treatment: We will compare overall satisfaction with treatment scores between the active and sham treatment groups (t-test).

Safety: We will tabulate AEs across all participants. This will include tabulating the number of participants for whom the event occurred, the rate of occurrence, and the severity and relationship to the study device.

Effectiveness: Change in HAM-A score: We will compare the change in HAM-A score between the active and sham treatment groups (t-test).

Effectiveness: Change in GAD-Q-IV score: We will compare the change in GAD-Q-IV score between the active and sham treatment groups (t-test).

Effectiveness: Change in BAI score: We will compare the change in BAI score between the active and sham treatment groups (mixed models).

Effectiveness: Change in daily anxiety severity self-report: We will compare the change in daily anxiety severity scores between the active and sham treatment groups (mixed models).

Effectiveness: Change in daily anxiety interference self-report: We will compare the change in daily anxiety interference scores between the active and sham treatment groups (mixed models).

Effectiveness: Change in anxiety severity self-report as an immediate result of treatment: We will compare the short-term effect of Empower treatment on anxiety severity score (% change for post-treatment score vs. pre-treatment score) (repeated measures ANOVA with Tukey correction, active vs. sham treatment group).

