Effectiveness: Medication use: We will calculate average benzodiazepine use per week. We will compare medication use between the active and sham treatment groups (mixed models).

Effectiveness: Change in HAM-D score: We will compare the change in HAM-D score between the active and sham treatment groups (t-test).

Effectiveness: Change in PHQ-9 score: We will compare the change in PHQ-9 score between the active and sham treatment groups (t-test).

Effectiveness: Change in PCL-5 score: We will compare the change in PCL-5 score between the active and sham treatment groups (t-test).

Effectiveness: Change in PSQI score: We will compare the change in PSQI score between the active and sham treatment groups (t-test).

Effectiveness: Change in SF-12 score: We will compare the change in SF-12 score between the active and sham treatment groups (t-test).

Blinding: We will statistically assess blinding for the active and sham treatment groups using the blinding index from Bang et al.

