## 15.5 Randomization and Sample Size

At enrollment, participants will be randomized (1:1, [REDACTED] stratified by sex) to the active or sham stimulation. Participants will also be randomized for the body side that they should apply stimulation to first (right vs. left, 1:1 simple randomization). Men and women will be randomized separately.

As a pilot study, our primary goal is to demonstrate feasibility for GAD treatment. Accordingly, the study sample size is based on similar pilot GAD studies in the literature. For two rTMS studies, each treatment arm had 12-25 participants, with an average of 15 participants. To be consistent with these studies, we will enroll 15 participants per treatment arm, for a total of 30 participants.

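### Seven secondary outcomes, HAM-A among them, are compared by an unadjusted t-test on change; ANCOVA on the Visit 1 score would give more precision from data already collected

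*Combined protocol and SAP*

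**What the plan says.** Section 15.4 (Analysis of Secondary Endpoints) states for HAM-A: "We will compare the change in HAM-A score between the active and sham treatment groups (t-test"). For HAM-D it states: "We will compare the change in HAM-D score between the active and sham treatment groups (t-test"). GAD-Q-IV, PHQ-9, PCL-5, PSQI and SF-12 get the same test, which makes seven outcomes. BAI, the daily VAS scores and medication use go to mixed models, and the immediate pre/post change to repeated-measures ANOVA, so this point does not concern them.

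Baseline exists for all seven. Section 10.1 (Visit 1) lists "Perform clinician-administered assessments (HAM-A and HAM-D) and participant-reported survey (PCL-5") and then "Complete self-report surveys (GAD-Q-IV, PHQ-9, PSQI, SF-12"), both before the randomisation step. Section 10.3 repeats all seven scales at Visit 3.

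The only covariate Section 15.4 mentions is time since the last benzodiazepine dose, to be added if its relationship with an endpoint is significant. Sections 8.1 and 15.5 stratify the randomisation by sex: "Men and women will be randomized separately to ensure that the distribution of men and women in the active and sham arms are consistent". The seven comparisons leave sex out.

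**The concern.** A change score fixes the slope of follow-up on baseline at 1. ANCOVA estimates that slope. When the true slope is below 1, the change score over-corrects for baseline and carries part of any chance baseline difference into the treatment estimate. This is extra variance, not bias, and the t-test's standard error already reflects it.

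At 15 per arm, chance baseline differences are not small, and withdrawn participants are not replaced (Section 12.4). Section 5.2 gives these outcomes a purpose: "All of these secondary endpoints provide valuable information on the effectiveness of the Empower Neuromodulation System for GAD treatment". Section 5.1 looks ahead to a pivotal study. Wider intervals than necessary would make the estimates a weaker basis for planning it.

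**Working it through.** **Inputs from the documents.** 15 per arm, 30 in total (Section 15.5); sex-stratified 1:1 allocation; about 64% women among US adults with GAD (Section 8.1). The sample size follows the arm sizes of two earlier studies, with no alpha, power, effect size, SD or correlation, so only its arithmetic can be reproduced: 2 × 15 = 30, and 30/(1 − 0.5) = 60 screened.

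**Assumptions.** Correlation ρ between Visit 1 and Visit 3 of 0.3 to 0.6; equal SDs at the two visits, scaled to 1; two-sided alpha 0.05; 19 women and 11 men (0.64 × 30 = 19.2).

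**Step 1, large-sample variance.** Var(change) = residual variance + (1 − slope)² × Var(baseline). With equal SDs this is (1 − ρ²) + (1 − ρ)² = 2(1 − ρ). ANCOVA leaves 1 − ρ². The ratio ANCOVA/change is (1 + ρ)/2, so the change score loses (1 − ρ)/2 of the information: 35% at ρ 0.3 and 20% at ρ 0.6.

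**Step 2, small-sample cost.** Estimating two covariates at N=30 multiplies the ANCOVA variance by (N − 3)/(N − 5) = 27/25. If stratification keeps sex nearly balanced between arms, the cost is close to that of one covariate, 27/26.

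| ρ | Loss, large sample | Loss at N=30, factor 27/25 | Loss at N=30, factor 27/26 |
|---|---|---|---|
| 0.3 | 35% | 1 − 0.65 × 1.08 = 29.8% | 32.5% |
| 0.4 | 30% | 1 − 0.70 × 1.08 = 24.4% | 27.3% |
| 0.5 | 25% | 1 − 0.75 × 1.08 = 19.0% | 22.1% |
| 0.6 | 20% | 1 − 0.80 × 1.08 = 13.6% | 16.9% |

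Simulation at 15 per arm agrees: about 30% to 13% with sex unbalanced, and 32% to 17% with sex stratified. The simulated type I error of the planned t-test is about 5%.

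**Step 3, power at ρ = 0.4 (noncentral t).** The SE of the change-score difference is √(1.2 × 2/15) = 0.400 on 28 df. The ANCOVA SE is √(0.84 × 1.08 × 2/15) = 0.348 on 26 df, or 0.341 with sex nearly balanced.

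| True difference | t-test on change | ANCOVA |
|---|---|---|
| 0.8 SD | 49% | 60–62% |
| 0.5 SD | 23% | 28–29% |
| 0.33 SD | about 12% | 15% |

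Section 1.1 quotes g of about 0.3 to 0.5 for existing treatments. Neither analysis has adequate power there.

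**Step 4, chance imbalance.** A one-SE baseline difference is √(2/15) = 0.37 SD. It moves the change-score estimate by (1 − ρ) × 0.37: 0.26 SD at ρ 0.3 and 0.15 SD at ρ 0.6.

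**Step 5, entry cut-offs.** HAM-A has an entry floor of 18. HAM-D and PCL-5 are capped by exclusion at 18 or more and 34 or more (Sections 6.2 and 6.3). Truncation reduces Var(baseline) in the step 1 formula; slope and residual variance are held fixed, and ρ is the untruncated value. The documents do not say where the cuts fall in the source population, so three positions are shown for ρ 0.3 to 0.6 at N=30.

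| Position of the cut | Var(baseline) | Loss from the change score |
|---|---|---|
| 1 SD from the mean, keeping about 84% | 0.63 | 7% to 22% |
| At the mean | 0.36 | 1% to 13% |
| 1 SD from the mean, keeping about 16% | 0.20 | −3% to 6% |

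Example, cut at the mean, ρ 0.3: Var(change) = 0.91 + 0.49 × 0.363 = 1.088, and 1 − (0.91/1.088) × 27/26 = 13%. At ρ 0.4 with this cut, power for 0.8 SD is 57% against 60–62%.

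**Step 6, break-even without truncation.** (1 + ρ)/2 × 27/25 = 1 gives ρ = 50/27 − 1 = 0.85. With the baseline score alone, ρ = 52/27 − 1 = 0.93. At ρ 0.85 with the cut at the mean, ANCOVA is about 1% to 5% worse: (0.2775/0.2857) × 27/26 = 1.009, and with 27/25 it is 1.049.

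**Step 7, dropout.** At an assumed 12 per arm the two-covariate factor is 21/19. The loss at ρ 0.5 becomes 1 − 0.75 × 21/19 = 17% instead of 19%.

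**The case against.** The other side has a fair case. The planned test is valid and already uses the Visit 1 score by subtraction. These are secondary outcomes in a feasibility pilot that was not sized for them, and no success criterion hangs on any of the seven. Every magnitude depends on an assumed correlation.

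The most visible outcome, HAM-A, has an entry floor, so the untruncated power figures may flatter the gain for it. If the cut is at the mean, the advantage at ρ 0.4 shrinks to about 3 to 4 points for a 0.8 SD difference and about 1 to 2 points for 0.5 SD. If only a narrow slice of the distribution remains, ANCOVA can be level or marginally worse. Dropout reduces the gain a little further. Adding sex costs a degree of freedom and lowers the break-even correlation from 0.93 to 0.85.

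All of this stands as a limit on the size of the gain, chiefly for HAM-A, HAM-D and PCL-5. It does not remove the point. GAD-Q-IV, PHQ-9, PSQI and SF-12 have no entry cut-off of their own, and the possible loss from ANCOVA is a few percent against a plausible gain of 14% to 30% where the baseline is not truncated. That the sample is small and fixed is a reason to use the baseline, not to leave it out.

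**Conclusion.** The concern holds. Seven outcomes are tested on unadjusted change although a pre-randomisation score exists for each, and no part of the plan adds a baseline covariate. The cost is lost precision on secondary outcomes; validity, the primary endpoints and the sample size are unaffected.

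With equal SDs and ρ between 0.3 and 0.6, the change score forgoes roughly 30% to 14% of the information at N=30, or 32% to 17% if sex is nearly balanced. For the three scales with entry cut-offs the gain is smaller and could vanish. Adjustment does not rescue power for effects of 0.3 to 0.5 SD. The direction of the advantage is secure below ρ of about 0.85 when the baseline is not sharply truncated; its size rests on assumptions that the documents cannot settle. This is a change that should be made, not a defect that invalidates the plan.

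**What to change.** In Section 15.4, for these seven outcomes only, replace the t-test on change with ANCOVA of the Visit 3 score on treatment group, Visit 1 score and sex. Report the adjusted difference with its 95% CI. Sex is included to match the stratified randomisation, not because it is expected to add much precision. Keep the change-score t-test as a sensitivity analysis, and fix the model before unblinding so that there is no choice between adjusted and unadjusted results afterwards.

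The cost is SAP wording and two error degrees of freedom (28 to 26). No new data, visits or participants are needed. A scale with a very narrow baseline range, or a correlation near 0.85, will show little or no benefit.

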#### ***9.1.7.1 Daily Surveys***

The daily survey questions will be completed on the Empower app and include questions about non-scheduled anxiety medication use (e.g. benzodiazepine dose taken over the past 24 hours and day/time of last dose), anxiety severity over the past 24 hours, anxiety interference with daily life over the past 24 hours, and anxiety severity at the present time. For anxiety severity, the participant will be asked to rate it on a 100-point visual analog scale (VAS) [0="No anxiety at all" through 100="Severe Anxiety"]. For anxiety interference with daily life, the participant will be asked to rate it on a 100-point visual analog scale (VAS) [0="Not at all" through 100="Extreme"].

The app will guide the participant to complete the daily survey prior to self-administering the first treatment session of each calendar day. Immediately after the session, the participant will also be asked about anxiety severity at the present time and if a tingling sensation was felt on the skin at the site of stimulation application to confirm effective nerve stimulation.

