#### **9.1.11 Adverse Events**

Information regarding occurrence of AEs and serious AEs (SAEs) will be captured throughout the study. Duration (start and stop dates), severity/grade, outcome, treatment and relation to study device and procedures will be recorded on the case report form (CRF).

If the participant's skin becomes too irritated to comfortably carry out the treatment sessions, the participant will be instructed to refrain from administering a treatment session until the skin is no longer irritated.

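### The immediate-effect endpoint is analysed as percent change on a VAS where 0 is a valid pre-score, by an ANOVA poorly suited to uneven daily series; the plan's own mixed model on VAS points is a better main analysis

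*Combined protocol and SAP*

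**What the plan says.** Section 5.2 lists the endpoint as "Effect of treatment group on change in self-reports of anxiety severity immediately after vs. before treatment (via 100-mm VAS"). Section 15.4 turns this into the percent "change for post-treatment score vs. pre-treatment score) (repeated measures ANOVA with Tukey correction, active vs. sham treatment group").

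Section 9.1.7.1 describes the data. The anxiety scale is anchored "0='No anxiety at all' through 100='Severe Anxiety". The pre-session rating belongs to a daily survey, and the app guides the participant to "complete the daily survey prior to self-administering the first treatment session of each calendar day". For the second rating: "Immediately after the session, the participant will also be asked about anxiety severity at the present time". The visible text therefore yields at most one clear pre/post pair per calendar day.

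Section 15.4 also sets a default, to apply unless another method is noted: "for daily and weekly metrics, we will use a random-intercept linear mixed model with restricted maximum likelihood". The closest sibling endpoint follows it: "We will compare the change in daily anxiety severity scores between the active and sham treatment groups (mixed models"). Daily anxiety interference is handled in the same way. The immediate-effect endpoint is the daily VAS measure taken out of that default.

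The visible text gives no rule for a pre-score of 0 and does not name the repeated factor.

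**The concern.** The chosen metric divides by a quantity that may validly be 0. Such pairs must be dropped, assigned a value or offset, and that choice could be made after the data are seen. A zero rule alone would not cure the metric, because pairs starting just above 0 still give very large percentages. A fall is limited to -100%, whereas a rise from 1 can reach 100 x (100 - 1)/1 = 9,900%.

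The method adds a second difficulty. Daily series will differ in length between participants, for three reasons visible in the plan:
- Visit 3 may fall anywhere within Day 43 ± 7.
- Sessions will be missed. Section 12.3 sets the non-compliance trigger only at less than one session in two weeks.
- With skin irritation, "the participant will be instructed to refrain from administering a treatment session until the skin is no longer irritated".

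A repeated measures ANOVA needs these series to be aligned or summarised first, and the plan does not say how. At stake is how clearly this pilot reads the immediate anxiolytic effect.

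**Working it through.** The plan gives no VAS mean, SD, effect size or significance level for this endpoint, so there is no figure of its own to reproduce.

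**1. The metric.** Percent change = 100 x (post - pre)/pre. The same 5-point rise gives:

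| Pre | Post | Points | Percent |
|---|---|---|---|
| 0 | 5 | +5 | undefined |
| 1 | 6 | +5 | +500 |
| 5 | 10 | +5 | +100 |
| 50 | 55 | +5 | +10 |
| 60 | 65 | +5 | +8.3 |

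**2. Weight of one pair.** Take 42 daily pairs (Days 1 to 42) averaged per participant, and 15 participants per arm (Section 15.5). One 1-to-6 pair moves the participant mean by 500/42 = 11.9 percentage points and the arm mean by 11.9/15 = 0.8. The same rise from 60 moves the participant mean by 8.33/42 = 0.2. The first pair counts as much as 500/8.33 = 60 of the second.

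**3. Share of undefined pairs (assumed inputs).** For a mean pre-score m and between- and within-person SDs sb and sw, the share scored 0 after rounding is approximately the normal tail Φ((0.5 - m)/√(sb² + sw²)):

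| SD between/within | m = 35 | m = 45 | m = 55 |
|---|---|---|---|
| 18/18 | 8.8% | 4.0% | 1.6% |
| 15/15 | 5.2% | 1.8% | 0.5% |
| 12/10 | 1.4% | 0.2% | 0.02% |

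For example, at m = 35 and 18/18: (0.5 - 35)/25.46 = -1.355, a tail of 8.8%.

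**4. Series length.** With one pair per day up to the day before Visit 3, the window allows 43 - 7 - 1 = 35 to 43 + 7 - 1 = 49 pairs, before any missed or paused days.

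**5. Tukey.** With two group means and 28 df (30 - 2), the critical value is q(0.95; 2, 28)/√2 = 2.05, the same as the ordinary t value. The correction does nothing for the contrast the plan names.

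**6. The mixed model on uneven series (assumed inputs).** Simulated series ran for 35 to 49 days, completion was 40% to 100% by person, and 20% of participants had a 7-day gap (2,000 replicates). With no true difference, the estimate in points stayed within 0.05 of 0. Rejection at a nominal 5% was 4.9-5.9% with a t reference on 28 df and 5.9-6.8% with a normal reference, hence the small-sample reference in the fix.

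**7. Points against percent (assumed inputs).** Settings: 15 per arm, 42 pairs with 90% completed, mean pre-score 35, 45 or 55, SDs 18/18 or 12/10, person-level response SD 3 to 6, residual SD 10, and changes of -8 against -3 points. The test was a t-test on participant means, with zero pairs dropped from percent change. Differences in power, in percentage points:
- Additive effect: points lead by 4 to 16.
- Effect and noise both proportional to the pre-score: percent leads by 3 to 19.
- Only the effect proportional: from 30 in favour of points to 3 in favour of percent.

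**8. Shift in the points estimate.** Suppose active-arm anxiety falls steadily by 20 points over the study, about 10 on average, and both arms have the same proportional response, 5 points at the starting mean. The active arm's point change is then smaller by about 10 x 5/45 = 1.1 points at a mean of 45 (10 x 5/35 = 1.4 at 35; 10 x 5/55 = 0.9 at 55). Simulation gave +0.9 to +1.5 points without clipping at the scale ends and +1.0 to +1.8 with it (rejection 8-17%). Most of the shift is therefore scale and a smaller part is floor. With equal true point changes it was +0.1 to +0.8 (rejection 4-8%). These shifts go against the device. Percent change also moved in these settings, by -7.5 to +8.0 percentage points (rejection 4-15%).

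**The case against.** The strongest reply is that percent change and ANOVA are both permitted choices, so one sentence stating a zero rule and another naming the repeated factor would suffice, and the rest is preference. If the response really is proportional to the pre-score, percent change is the natural scale, and points would understate the active arm once its daily anxiety has fallen.

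Part of this stands. The scale is a genuine trade-off, as steps 7 and 8 show, so percent change should stay as a supportive result. But a zero rule leaves the instability at pre-scores just above 0, and naming a factor does not make ANOVA a good fit to unequal series. The plan already holds a method that avoids both problems.

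A reader might infer more than the documents support:
- *Sections 5.2 and 15.4 contradict each other.* They do not. The word *change* in Section 5.2 admits points or percent.
- *The ANOVA breaks the mixed-model default.* It does not. The default yields wherever another method is noted.
- *Most participants would be lost.* With day as the factor, complete cases only and independent days, 30 x 0.95^42 = 3.5 participants would remain at 95% daily completion. The plan specifies neither that factor nor complete cases, and weekly means would keep nearly everyone (30 x (1 - 0.1^7)^6 = 30.0 even at 90%).
- *Tukey would impose a heavy penalty.* That needs a set of group-by-time comparisons that the plan does not describe.
- *Points are generally more powerful.* Step 7 shows otherwise.

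Redaction also limits the point. Treatment is twice daily, but Section 9.1.8 and parts of Section 4.4 are blacked out, so whether second sessions carry a pair cannot be seen and is not a fault of the plan.

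**Conclusion.** The concern holds as a minor, cheap improvement. Three things rest on the text and simple arithmetic alone: the metric has no value at a permitted pre-score, it is unstable just above it, and Tukey does nothing for the stated contrast. That repeated measures ANOVA fits poorly rests on series of unequal length, which the visit window, missed sessions and skin pauses make very likely.

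The size of the effect on the result is not known. The 0% to 9% range for undefined pairs depends on assumed means of 35 to 55 and the assumed SDs in step 3, and nothing in the documents shows that the conclusion would change. The case for points is that they are always defined and fit both the wording of Section 5.2 and the model used for the sibling endpoints; it is not that they always have more power. The issue touches one secondary endpoint in a 30-person pilot. Adherence and SUS are unaffected.

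**What to change.** Amend the paragraph in Section 15.4 as follows:
- Main analysis: post-minus-pre change in VAS points, all observed pairs, in the random-intercept REML mixed model with treatment group as fixed effect and participant as random intercept.
- Test the group effect against a small-sample t reference (about 28 df with 30 participants).
- Remove the Tukey correction.
- State which daily sessions supply a pair: the first of each calendar day only, or the second as well if it is rated before and after.
- Report percent change as supportive, with the rule for a pre-score of 0 fixed before unblinding (for example, exclude the pair) and the number of such pairs given per arm.

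The cost is wording only; data collection does not change. The main result would be in points instead of percent. Points can lose power if effect and noise both scale with the pre-score. They can also shift against the device if response is proportional and active-arm anxiety falls over the study, mainly through scale with a smaller floor effect. Reporting the supportive percent result beside the main one lets a reader see whether the two scales disagree.
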